9.6.3 Laboratory Test Results

List of tests to be performed by the local laboratory for this study is as defined below.

Local Laboratory: Chemistry	Local Laboratory: Coagulation	Local Laboratory: Urinalysis	Local Laboratory: Hematology	Other Labs
Sodium Potassium Chloride Albumin Total Calcium BUN Creatinine Glomerular filtration rate Uric acid Total bilirubin Direct bilirubin ALP LDH AST (SGOT) ALT (SGPT) Amylase Lipase	PT/INR aPTT	Blood Protein Glucose	RBC Hemoglobin Hematocrit Platelets WBC Differential • Absolute Neutrophils • Neutrophils • Segmented Neutrophils • Bands/stabs • Eosinophils • Basophils • Blasts • Lymphoblasts • Lymphoblasts • Lymphocytes • Monocytes • Myeloblasts • Promyelocytes • Myelocytes • Myelocytes • Metamyelocytes	Bone marrow histology and MRD CSF analytes • CSF Glucose • CSF Protein • CSF White Blood Cells • CSF Blasts Local Laboratory : Serum and/or Urine Pregnancy

ALP = alkaline phosphatase; ALT = alanine aminotransferase; AST = aspartate aminotransferase; BUN = blood urea nitrogen; CSF = cerebrospinal fluid; INR = international normalized ratio; LDH = lactate dehydrogenase; MRD = minimal residual disease; PT = prothrombin time; aPTT = activated partial thromboplastin time; RBC = red blood cell count; SGOT = serum glutamic-oxaloacetic transaminase; SGPT - serum glutamic-pyruvic transaminase; WBC = white blood cell count

Summary statistics over scheduled visits for actual values, changes from baseline of selected laboratory parameters listed below will be presented. Shift tables between the post-baseline and baseline values for selected laboratory parameters will be also provided for subjects in the Safety Analysis Set.

Summary statistics tables: lymphocytes, neutrophils, WBC, platelets, hemoglobin, albumin, AST, ALT, bilirubin, corrected calcium, potassium, lipase, amylase, ALP, IgG, creatinine

Shift tables: lymphocytes, hemoglobin, corrected calcium, potassium, neutrophils, WBC, platelets, albumin, AST, ALT, bilirubin, lipase, amylase, creatinine

The subject incidence of potential cases of Hy's Law will be summarized. See Appendix A as a guide for table shell.

9.6.4 Vital Signs

Vital sign data are captured using both CWHMS during MDMP period and on eCRF during in-clinic visits (i.e. at screening, C2D1 and C2D29). Subject vital signs **captured on eCRF** will be summarized over time. A summary of the subject incidence with abnormal changes in vital signs will be presented for subjects in the SAS. Vital signs will include BP, **Respiratory rate**, **Pulse rate** and axillary temperature.

Abnormal changes in vital signs will be defined as follows:

- Systolic BP <=100 mmHg or >=20% reduction from baseline
- Temperature >= 38.0° C (100.4° F)
- Respiratory rate <=10 or >=25
- Pulse rate <=60 or >=150

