Study Day within Cycle	D- 21 to D-1	D-14	D- 3 to				D29 (± 7 d ays)	D1	D2	D29 (± 3 days)	End of C2 Clinical Assessment (D29)	(C3, optional cycle)	(C4, optional cycle)	(30 days + 3 days post last dose blinatumomab)	
Clinical Chemistry (contin	nued)														
Serum and/or Urine pregnancy test (females of childbearing potential only)															Additional on-treatment pregnancy testing may be performed at the investigator's discretion if there is suspicion that a female subject is pregnant or per local laws and regulations. A highly sensitive (urine or serum) pregnancy test should be completed at screening and within 7 days of initiation of investigational product for females of childbearing potential.
Urinalysis	Χ														
Bone marrow MRD							Х								According to institution practice.
DIGITAL HEALTH Eligibility for home monitoring and wearables		Х													
CWHMS kits delivered to site	Х														Monitoring device kits will be sent to site at site initiation. Each kit will have duplicate devices and an oral thermometer to be used as needed.
Subject home monitoring device training.		Х													
Caregiver eligibility and device monitoring training		Х													

Page 4 of 7

Date: 21 April 2022 Page 24 of 108

Table 1-2. Schedule of Activities

PROCEDURE		reenir 21 day	•	су	cle 1	(C1)				cycle 2 (C2	2)	cycle 3 (C3)	cycle 4 (C4)	EOS	Notes
Study Day within Cycle	D- 21 to D-1	D-14 to D-7	3 to	D2	D3	D4	D29 (± 7 d ays)	D1	D2	D3	D29 (± 3 days)	End of C2 Clinical Assessment (D29)	(C3, optional cycle)	(C4, optional cycle)	(30 days + 3 days post last dose blinatumomab)	
DIGITAL HEALTH																
PI/Site device monitoring training		x														Site training will be completed at initiation and during the screening period for the first subject is enrolled. Training may be required for first subject only. Any subsequent training will be requested ad hoc
Subject home trial period of CWHMS assessed for 24-48 hours to determine eligibility.		X														Recommend to be completed at least 1 week prior to start of treatment (during screening, subjects should test wearing of devices and data transmittal for a minimum of 24 hours). During this screening device testing period, the study doctor will not be monitoring the device. The subject or caregiver must immediately contact the study doctor directly if the subject is feeling unwell during the screening period.

Page 5 of 7

Date: 21 April 2022 Page 25 of 108

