9.4.2.3.4 Vital Signs

A summary of the subject incidence with abnormal changes in vital signs will be presented for subjects in the SAS. Vital signs to include: BP, **respiratory rate**, **pulse rate**, and axillary temperature.

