4.2 Subgroups

Due to small sample size, subgroup analysis will not be performed.

5. Definitions

Age at Enrollment:

Subject age at enrollment will be collected in years in the clinical database.

Adverse Event During the MDMP

Adverse event during the MDMP is defined as an adverse event that started within 72 hours after the first dose of blinatumomab in cycle 1 and within 48 hours after the first dose of blinatumomab in cycle 2.

For adverse events with missing start time, the adverse event during the MDMP is defined as an adverse event that started within 3 days after the first dose date of blinatumomab in cycle 1 and within 2 days after the first dose date of blinatumomab in cycle 2.

Baseline

The baseline value will be defined as the value measured on day 1 of the first cycle before start of the first infusion of blinatumomab. If a cycle 1 day 1 value is not available, the latest value before the day 1 of the start of blinatumomab infusion may be used.

Cumulative Dose of Blinatumomab

The cumulative dose in μg is defined as the following with summation over infusions:

 \sum Duration of infusion [days] for each dose received × dose received [μ g/day].

Cumulative dose will be calculated within a cycle and across all cycles.

Duration of Therapy

For each infusion episode within a cycle, the duration of exposure will be calculated by subtracting the start date and time from the stop date and time. If either a start or stop time is missing, only the date portion will be used in calculating the duration of a specific

infusion. For each cycle, the duration will be the sum of the individual infusion durations within that cycle. For the entire study, the duration will be the sum of the durations across cycles. The duration will be rounded to the nearest day.

End of Study

The end of study date is defined as the date when the last subject across all sites is assessed or receives an intervention for evaluation in the study (i.e. last subject last visit).

End of Study Visit

The end of study visit will occur 30 days (\Box 3 days) after the last dose of blinatumomab is given. The end of study visit will occur after cycle 3 or 4 for subjects who chose these optional cycles. End of study visit date for each subject will be recorded on the End of Study CRF page.

Enrollment Date

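### SAP 9.6.4 counts fixed vital-sign levels as abnormal changes even in subjects who already met them before dosing; in practice this concerns pulse <=60 and SBP <=100

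*SAP*

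**What the plan says.** Protocol 9.4.2.3.4 states: "A summary of the subject incidence with abnormal changes in vital signs will be presented for subjects in the SAS". SAP 9.6.4 repeats the commitment and supplies the definition, introduced by "Abnormal changes in vital signs will be defined as follows". Its limbs include "Systolic BP <=100 mmHg or >=20% reduction from baseline", "Respiratory rate <=10 or >=25" and "Pulse rate <=60 or >=150", plus a temperature of 38.0 °C or more.

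The SAP does define a baseline, in section 5: "The baseline value will be defined as the value measured on day 1 of the first cycle before start of the first infusion", with the latest earlier value as fallback. Within the abnormality list, only the percentage limb for systolic pressure uses it. SAP 9.6.4 also lists where vital signs are captured: by the wearable system during the mandatory device monitoring period (MDMP), and on the eCRF at screening, C2D1 and C2D29. It does not say which source feeds the incidence table, nor that only post-dose values count.

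**The concern.** A table of changes should count something that differs from the subject's own starting point. Because SBP <=100 is joined to the percentage limb by an or, it counts whatever the starting pressure was. The pulse, respiratory-rate and temperature limits have no baseline term at all. A subject who is habitually bradycardic or has low-normal pressure is therefore entered as having an abnormal change on blinatumomab without any change having occurred.

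The study has one arm, so no control incidence is available for comparison. A count that includes pre-existing values is biased upward, and a reader of the table cannot tell by how much.

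**Working it through.** **1. Which limbs use baseline**

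| Criterion in SAP 9.6.4 | Refers to baseline? |
|---|---|
| SBP reduced by 20% or more | Yes |
| SBP <=100 mmHg | No |
| Pulse <=60 or >=150 | No |
| Respiratory rate <=10 or >=25 | No |
| Temperature >=38.0 °C | No |

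**2. Can such subjects enrol?** Protocol 5.1 and 5.2 contain no numerical limit on pulse or blood pressure. The exclusion for acutely ill cardiac patients at risk of life-threatening arrhythmia does not reach a resting pulse of 58.

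**3. How the SAP treats other safety data.** Treatment-emergent adverse events must start on or after the first dose (section 5). Laboratory values get change-from-baseline summaries and shift tables (9.6.3). The Hy's Law shell has separate pre-infusion and on-study rows (Appendix A). The fixed vital-sign criteria have no equivalent.

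**4. The plan's own figures.** No expected incidence of abnormal vital signs is stated, so there is nothing to reproduce for this table. The one sample-size figure, an upper 95% limit of 53.5% with 45 subjects, does reproduce: the exact interval for 17/45 has an upper limit of 53.46%. It is not affected by this point.

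**5. Share meeting a limit before dosing (assumed inputs).** Assume normal distributions: pulse mean 70 to 80, SD 12; SBP mean 115 to 125, SD 15; respiratory rate mean 16, SD 2.5; temperature mean 36.7 °C, SD 0.35. With Φ the standard normal distribution function, the share at or below a limit is Φ((limit − mean)/SD).

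- Pulse <=60: mean 80 gives Φ(−1.67), about 5%; mean 75 gives Φ(−1.25), about 11%; mean 70 gives Φ(−0.83), about 20%.
- SBP <=100: mean 125 gives Φ(−1.67), about 5%; mean 120 gives Φ(−1.33), about 9%; mean 115 gives Φ(−1.00), about 16%.
- Respiratory rate <=10: Φ(−2.4), about 0.8%. Respiratory rate >=25, temperature >=38.0 °C and pulse >=150: about 0%.

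Only pulse <=60 and SBP <=100 contribute materially.

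**6. Effect on the table: two post-dose clinic visits, no drug effect.** Each reading is the mean plus a subject effect plus reading error, with within-subject correlation 0.5 or 0.7 (400,000 simulated subjects). The SAP rule is applied as written, then with each absolute criterion counted only if unmet at a single baseline reading. The 20% limb is kept in both. All subjects are in the denominator, so the two columns compare directly; small gaps in the difference column are rounding.

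| Mean pulse / SBP | Correlation | As written | With baseline condition | Flagged only because it is missing | Of 45 |
|---|---|---|---|---|---|
| 80 / 125 | 0.5 | 20.8% | 17.4% | 3.4% | 1.5 |
| 75 / 120 | 0.5 | 34.1% | 26.1% | 7.9% | 3.6 |
| 70 / 115 | 0.5 | 51.6% | 35.5% | 16.1% | 7.2 |
| 80 / 125 | 0.7 | 17.0% | 11.9% | 5.1% | 2.3 |
| 75 / 120 | 0.7 | 29.7% | 18.8% | 10.9% | 4.9 |
| 70 / 115 | 0.7 | 47.0% | 26.7% | 20.4% | 9.2 |

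A second set of assumptions has less spread between subjects (pulse SD 10, SBP SD 12 to 13), within-subject SDs of 5 to 6 and 7 to 8, and means from 85/128 down to 70/118. It uses only pulse <=60 and the two SBP limbs. It gives 7% to 39% as written and 5% to 20% with the condition, a difference of about 2 to 18 points. Of those flagged for pulse <=60, 31% to 55% already met it at baseline; for SBP <=100, 33% to 45%.

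Across both sets the range is about 2 to 20 points: 0.02 × 45 = 0.9 and 0.20 × 45 = 9 subjects.

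**7. If device values were used instead.** The MDMP lasts 72 + 48 = 120 hours, or 120/3 = 40 three-hourly medians. With the first set of means and correlation 0.7, the table as written flags 60% to 89% and the baseline condition lowers this only to 54% to 75%. Most of that count is ordinary variation over many readings.

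**The case against.** Several points on the other side stand.

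- **Other outputs exist.** A reader might infer that this is the only view of vital-sign abnormality. It is not: SAP 9.6.1 tabulates subjects with alarms by physiological reason, SAP 9.6.4 summarises eCRF vital signs over time, and adverse events carry an onset rule. The alarm table, however, has no baseline condition either, and the summary over time gives group values, so neither corrects this count.
- **The limits are not only alert settings.** Protocol Appendix 8 defines hypotension for this study as SBP <=100 or a 20% fall, and calls pulse >=150 and respiratory rate >=25 severe. That supports the level as a definition of a state. It does not make an unchanged level a change.
- **The large device-based rates are not evidence for this point.** A reader might attribute a no-drug flag rate of 60% to 89% to the missing baseline condition. Step 7 shows that the condition removes only a part. Those rates also assume 40 pressure readings, although the protocol lets the interval extend to 6 hours after the first 24 hours, and SAP 9.6.4 does not say that device values feed the table.
- **Temperature and respiratory rate** share the wording flaw but add almost nothing.
- **The drug-free screening wear period** looks like a ready comparator, since "during screening, subjects should test wearing of devices and data transmittal for a minimum of 24 hours". But the protocol presents it as eligibility testing, and nothing confirms that its full record reaches the analysis database.

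**Conclusion.** The definition does not match the table's title: a value unchanged from before dosing counts as an abnormal change, and pre-dose records are not excluded. That follows from the text and needs no assumption.

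The size does rest on assumptions, because the documents give no baseline vital-sign data. Under the ranges shown, with no drug effect and two post-dose clinic visits, about 2 to 20 percentage points of subjects (roughly 1 to 9 of 45) are flagged for this reason alone, nearly all through pulse <=60 and SBP <=100.

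It would go too far to infer that the trial's safety conclusion is compromised. This is a descriptive secondary table in a study without formal hypotheses; the primary endpoint, its exact interval and the sample size are untouched. Nor would the correction make the table specific to drug effect: some flags remain from reading-to-reading variation. The change is still worth making, because the count is wrong as defined and cheap to put right.

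**What to change.** In SAP 9.6.4:

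1. Count records after the first dose only.
2. Count an absolute-level criterion only if the subject did not meet it at baseline as defined in SAP section 5, with subjects not meeting it at baseline as the denominator.
3. Keep the 20% reduction in systolic pressure for all subjects.
4. Show subjects who already met a criterion on a separate line with their worst post-dose value, or give a baseline-to-worst shift table.

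Naming the data source for the table (clinic, device or both) in the same edit would help, since the no-effect rate depends heavily on it. A side-by-side tabulation of the screening wear period is optional, and only if those data are in the database.

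The cost is SAP wording, one derived flag and one extra line, with no new data collection. The downside is slightly smaller denominators that differ by criterion. Clinical alert limits are unchanged.

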9.6.5 Physical Measurements

Physical measurements (height, weight and BSA) will be summarized at baseline for all the subjects in SAS.

9.6.6 Electrocardiogram

The electrocardiogram (ECG) measurements from this clinical study were performed as per standard of care for routine safety monitoring, rather than for purposes of assessment of potential QT interval corrected (QTc) effect. Because these evaluations may not necessarily be performed under the rigorous conditions expected to lead to meaningful evaluation of QTc data; neither summaries nor statistical analyses will be provided, and these data would not be expected to be useful for meta-analysis with data from other trials.

9.6.7 Antibody Formation

Not applicable

9.6.8 Exposure to Investigational Product

Descriptive statistics will be produced to describe the exposure to blinatumomab for subjects in the SAS. The duration of therapy and the cumulative dose will be summarized.

The number and percent of subjects with dose modifications (eg, dose changes, dose interruptions) and reason for modification will be summarized. Analysis will be repeated for exposure during MDMP.

9.6.9 Exposure to Non-investigational Product

Not applicable.

9.6.10 Exposure to Other Protocol-required Therapy

Not Applicable.

9.6.11 Exposure to Concomitant Medication

The number and proportion of subjects receiving concomitant medications from study day 1 through EOS (30 days \pm 3 days post last dose of Blinatumomab) will be summarized by preferred term as coded by the World Health Organization Drug (WHODRUG) dictionary in the SAS.

9.7 Other Analyses

Not Applicable

9.7.1 Analyses of Pharmacokinetic or Pharmacokinetic/Pharmacodynamic Endpoints

Not applicable.

9.7.2 Analyses of Clinical Outcome Assessments

The Electronic Patient Reported Outcome (ePRO) will be assessed using EORTC QLQ-C30 at screening and Cycle 2 Day 1.

Descriptive statistics for the overall GHS/QoL domain, 5 functional domains, and 9 symptom domains will be presented at baseline and Cycle 2 Day 1. Descriptive statistics for change from baseline will also be reported at Cycle 2 Day 1.

Change from baseline at Cycle 2 Day 1 for GHS/QoL score will be categorized as follows (Kode and Chenna, 2019);

Improved	:	Change >=10
Stable	:	-10 < Change <10
Deteriorated	:	. < Change <=-10

Similar categorization with minimal important difference (MID) of 5 may also be reported. Counts and percentage of subjects within each category will be also be presented.

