Minimal/measurable residual disease is defined as the presence of leukemic cells not detectable by microscopy (< 5%) measured either by polymerase chain reaction (PCR) or flow cytometry. After achieving hematologic remission, the presence of MRD portends a poor prognosis for patients. In the Amgen trial MT103-203 (BLAST), 78% of subjects with MRD of B-precursor ALL achieved a complete MRD response to blinatumomab therapy. In this trial, 4 subjects (3%) had CRS (Common Terminology Criteria for Adverse Events [CTCAE] v4 grade 1, n = 2; grade 3, n = 2), all during cycle 1. Twelve (10%) and 3 subjects (3%) had grade 3 and 4 NT, respectively. Moreover, subjects with relapsed/refractory B-precursor ALL treated with blinatumomab in the Amgen trial 00103311 (TOWER) similarly had a low incidence of CRS and NT. In the 00103311 study the incidence of grade \geq 3 CRS and NT were 4.9% and 9.4%, respectively with 1% and 4.9% of subjects having their treatment discontinued due to CRS and NT, respectively (Kantarjian et al, 2017).

The current recommendation for blinatumomab treatment for subjects with MRD of B-precursor ALL is continuous intravenous infusion (CiVI) for 28 days, with the first

Date: 21 April 2022 Page 11 of 108

3 days in cycle 1 and the first 2 days in cycle 2 administered in the inpatient setting. This recommendation for hospitalization is primarily for safety concerns of CRS, NT, or other severe **adverse events (AEs)**.

This study **aims** to determine the safety and feasibility of complete outpatient blinatumomab administration for subjects with MRD of B-precursor ALL. The study will use the CWHMS that is comprised of **CH** wearable **device** worn on the **subject's** upper arm, **an** axillary temperature patch, a blood pressure cuff, a Wifi hub, tablet, **a** mobile phone **provisioned to the HCP**, and a platform will also be used to monitor subjects' vital signs while they are at home.

This study will include the following:

- Remote monitoring using CWHMS to measure vital signs and mobile electronic devices (tablet) to electronically communicate these vital signs with the HCP.
- The use of a Wi-Fi and cellular enabled platform for the transfer of data and communication between subject and HCP, to identify subjects at risk of developing grade 3 or 4 CRS, NT or other SAEs requiring hospitalization during the MDMP.

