Participants in this clinical investigation shall be referred to as "subjects." Approximately 45 subjects will participate in this study. Refer to Section 9.2 for sample size considerations.

Summary of Subject Eligibility Criteria

Adult subjects with B-cell precursor (BCP) ALL with minimal/measurable residual disease (MRD) defined as a bone marrow (BM) blast count < 5%.

For a full list of eligibility criteria, please refer to Section 5.1 to Section 5.2.

Treatments

Investigational Product

Amgen Investigational Product Dosage and Administration: Blinatumomab is administered as a CiVI.

A single cycle of blinatumomab treatment is 6 weeks in duration, which includes 4 weeks of blinatumomab CiVI followed by a 2-week treatment-free interval. The treatment-free interval may be prolonged by up to 7 days, if deemed necessary by the investigator. For subjects \geq 45 kg, blinatumomab will be administered at a dose of 28 μ g/day for all 4 weeks of continuous treatment. Subjects < 45 kg will be administered blinatumomab 15 μ g/m²/day (max 28 μ g/day).

Date: 21 April 2022 Page 16 of 108

Non-investigational Product

Non-Amgen Non-investigational Product Dosage and Administration:

Dexamethasone

Premedication with dexamethasone (or prednisone): Dexamethasone 16 mg (or equivalent prednisone 100mg) intravenously (IV): up to 6 hours before start of treatment in each treatment cycle. Subjects ≥ 45 kg will have 2 additional 8 mg doses (subjects < 45 kg will receive 2 doses of 5 mg/m² rounded to the nearest mg) of oral dexamethasone to use as needed for treatment of CRS symptoms only if instructed by HCP. It will be recommended that hospitalization be strongly considered for subjects who require interruption of blinatumomab for > 4 hours.

Procedures

Written informed consent must be obtained from all subjects before any study-specific screening procedures are performed. Study-specific procedures will occur according to the Schedule of Assessments (Table 1-2)

For a full list of study procedures, including the timing of each procedure, please refer to Section 8.2 and the Schedule of Activities in Table 1-2.

Statistical Considerations Sample Size Considerations:

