4.3 Justification for Investigational Product Dose

The blinatumomab dosing regimen selected for this study is 28 μ g/day for subject's \geq 45 kg (or 15 μ g/m²/day to a max of 28 μ g/day for subjects < 45 kg) under continuous intravenous infusion (CiVI) for a period of 28 days per treatment cycle, followed by a 14-day infusion free interval, as per approved dosing.

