6.5 Drug Administration

The drug administration should not be interrupted, if possible. In case of infusion interruption, due to any technical or logistic reason, the interruption should be as short as possible, and the infusion restarted at the earliest time possible. Every interruption longer than 1 hour should be documented. Administration of dexamethasone premedication will occur as described in Section 6.1.3. If the infusion is interrupted, if possible, the total infusion time should equal 28 days in each cycle.

A dose of up to 10% higher than the intended blinatumomab dose (per day) may not require specific intervention. In case of overdose or medication error, the infusion should be immediately stopped. Routine supportive and symptomatic care according to standard medical practice is recommended. Once the subject is stabilized and no clinically relevant safety findings due to blinatumomab are observed, resumption of blinatumomab at a correct dose can be considered after consultation with the Amgen medical monitor.

For blinatumomab, a dose of greater than 10% higher than the intended dose will be considered clinically important and classified as a serious adverse event under the criterion of "other medically important serious event" per Section 11.4. If the overdose results in additional AEs, the subject should be followed carefully until all signs of toxicity are resolved and the AEs should be recorded/reported per Section 11.4 of the protocol.

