2.1 Objectives and Endpoints

Objectives	Endpoints	
Primary		
• To determine the safety of outpatient blinatumomab administration, during the MDMP (defined as the first 3 days of cycle 1 and first 2 days of cycle 2 of outpatient blinatumomab infusion)	 Grade 3 and/or 4 CRS, NT or any adverse event (AE) requiring hospitalization (SAE) during MDMP. 	
Secondary		
• To determine the time from first detection of grade 3 or 4 vital sign, or significant clinical change to therapeutic intervention (any measurable action taken by or performed on the subject due to onset of the clinical parameters described above) during the MDMP	• Time (in minutes) from first onset of fever, hypotension, hypoxia, other grade 3 or 4 vital sign including seizure or neurological change (grade 3-limiting self-care activities of daily living [ADL]) to therapeutic intervention.	
 Evaluate the safety and tolerability of blinatumomab administered exclusively as an outpatient 	 Treatment-emergent adverse events (TEAE) and adverse events of interest in particular CRS and NT. 	
• Evaluate the impact of complete outpatient blinatumomab treatment on patient-reported outcome (PRO), global health status (GHS), and quality of life (QoL).	 European Organisation for Research and Treatment of Cancer (EORTC) validated electronic version of QLQ-C30. 	
Estimate healthcare resource utilization associated with treatment-related AEs	 Treatment-related TEAEs that resulted in hospitalizations. Treatment-related TEAEs that resulted in surgeries. Treatment-related TEAEs that resulted in the use of concomitant medications. Treatment-related TEAEs that resulted in the use of device/procedure intervention. 	

ADL = activities of daily living; AE = adverse event; CG = caregiver; CRS = cytokine release syndrome; EMS = Emergency Medical Service; EORTC = European Organisation for Research and Treatment of Cancer; GHS = global health status; HCP = Health Care Provider; IV = intravenous; MDMP = mandatory device monitoring period; NT = neurotoxicity; PO = by mouth; PRO = patient-reported outcomes; QLQ-30 = Quality of Life of Cancer Patients; QoL = quality of life; SAE = serious adverse event; TEAE = treatment-emergent adverse event.

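### Does a single post-baseline QLQ-C30 at Cycle 2 Day 1, two to three weeks after the infusion stops, defeat the patient-reported outcome objective?

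*SAP*

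**What the plan says.** SAP 9.7.2 fixes the schedule: "The Electronic Patient Reported Outcome (ePRO) will be assessed using EORTC QLQ-C30 at screening and Cycle 2 Day 1". Protocol Table 1-2 agrees, except that the first form may instead be completed before dosing on Cycle 1 Day 1. No form is scheduled during an infusion, after a monitored period, at the end-of-cycle-2 assessment or at the end of study. SAP 9.7.2 summarises scores and change from baseline at Cycle 2 Day 1 (C2D1). It sorts the global health status/QoL change into improved, stable or deteriorated at 10 points, and optionally at 5.

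The matching secondary objective in SAP 2.1 is to "Evaluate the impact of complete outpatient blinatumomab treatment on patient-reported outcome (PRO), global health status (GHS), and quality of life (QoL"). SAP 2.2 makes all analyses descriptive. SAP 6.5 admits to the PRO set only subjects with a baseline form and at least one later form.

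On timing, Protocol 4.3 describes 28 days of infusion "followed by a 14-day infusion free interval", and the synopsis (Protocol 1.1, Treatments) adds: "The treatment-free interval may be prolonged by up to 7 days". For interrupted infusions, Protocol 6.5 says that "if possible, the total infusion time should equal 28 days in each cycle". In the questionnaire printed in SAP Appendix B, items 6 to 28 stand under a past-week heading and items 29 and 30 are worded the same way. Items 1 to 5 carry no recall period.

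**The concern.** What is new in this trial is that the early days of treatment are given at home. The usual recommendation, as the synopsis describes it, has the first "3 days in cycle 1 and the first 2 days in cycle 2 administered in the inpatient setting". A reader would expect the quality-of-life objective to say something about those days, or at least about weeks on infusion. The one follow-up form instead asks about a week when the pump had been off for some time. A table showing mostly stable or improved subjects could be taken as evidence that home infusion is easy to live with, although respondents were describing a treatment-free week.

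There is also selection. A subject who stops before cycle 2 has no scheduled follow-up form and falls out of the PRO set, so the result describes those who went on. SAP 9.7.2 mentions neither point. At stake is an unsupported sentence in the report about one descriptive secondary endpoint. No decision rule depends on it.

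**Working it through.** **Inputs.** Infusion 28 days and interval 14 days (Protocol 4.3 and synopsis); interval extendable by 7 days (synopsis); recall 7 days (SAP Appendix B); cycle 1 monitored days 1 to 3 (SAP Section 5).

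**1. The plan's own figure.** 28 + 14 = 42 days, the stated 6-week cycle. It reproduces.

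**2. Recall window if the interval follows the end of infusion.** Let k be interruption days that are made up and g the interval. Last infusion day L = 28 + k. C2D1 = L + g + 1. Recall runs from C2D1 − 7 to C2D1 − 1. First recalled day minus L = g − 6, which is 8 for g = 14 and 15 for g = 21.

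| k | L | C2D1 (g = 14) | Recall | C2D1 (g = 21) | Recall | Infusion days recalled |
|---|---|---|---|---|---|---|
| 0 | 28 | 43 | 36–42 | 50 | 43–49 | 0 |
| 3 | 31 | 46 | 39–45 | 53 | 46–52 | 0 |
| 7 | 35 | 50 | 43–49 | 57 | 50–56 | 0 |
| 14 | 42 | 57 | 50–56 | 64 | 57–63 | 0 |

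The last monitored day of cycle 1 is day 3. With k = 0 and g = 14, 32 full days (4 to 35) lie between it and the recall window.

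**3. If C2D1 is held to the day 1 calendar.** Protocol 8.1.2 schedules later doses and visits from day 1, which can be read as holding C2D1 at day 43 with recall on days 36 to 42. Infusion days recalled = max(0, min(28 + k, 42) − 35): 0 for k up to 7, 3 for k = 10, 7 for k = 14. This reading cannot hold together with a full 14-day interval once infusion runs late. Zero overlap is therefore conditional on keeping the interval.

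**4. Which items are affected.** Items 6 to 30 make 25 of 30 items and 14 of 15 scales. Physical functioning (items 1 to 5) describes status when the form is completed. Table 1-2 does not mark the C2D1 form as predose, so at most part of one cycle 2 infusion day could enter.

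**5. Loss before cycle 2.** The documents do not size it. In BLAST, "Twelve (10%) and 3 subjects (3%) had grade 3 and 4 NT, respectively"; 3% of 45 is 0.03 × 45 = 1.35 subjects with grade 4 neurotoxicity. In TOWER, a relapsed/refractory population, the synopsis reports "1% and 4.9% of subjects having their treatment discontinued due to CRS and NT"; 45 × (0.01 + 0.049) = 2.7 if no subject counts twice. These cover only two causes. No rate is given for transplant, for other stopping, or for restart after a grade 3 event, so total loss is unknown.

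**6. What an added form on Cycle 1 Day 4 would recall.** Days −4 to −1 and 1 to 3, which is 4 pre-treatment days and 3 monitored days. It would reach 3 of 28 infusion days and share 4 of 7 days with a predose Cycle 1 Day 1 baseline.

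**The case for a change.** The case for changing the SAP is that the arithmetic is sound and the remedy cheap. A clearer table title, one sentence limiting the conclusion and one count of missing forms need no new data. SAP Section 10 has already realigned the resource-utilization endpoints with their objective, so such tidying has a precedent. Nothing in SAP 9.7.2 stops a reader from taking the category table as support for home infusion, and Protocol 2.3 does suggest that outpatient treatment may be more convenient.

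The factual part of this stands: the C2D1 change does not describe infusion days. The step to a plan change does not.

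- In SAP 2.1 the primary and time-to-intervention objectives are expressly tied to the monitored period. The PRO objective is not, and it does not mention infusion days. The synopsis counts the treatment-free interval as part of the cycle, so status at C2D1 is status after one complete outpatient cycle.
- The Amendment 1 rationale shows that the timing was chosen: one full cycle completed, with the tablet in the subject's hands. That is a fair operational trade-off.
- SAP 9.7.2 already names C2D1 for each summary and states no conclusion about infusion days that a caveat would correct.
- Loss before cycle 2 can largely be recovered. SAP 9.1 gives n for each summary, SAP 9.2 gives monitored-period completion and reasons for stopping, and SAP Section 5 derives exposure by cycle for the summaries in SAP 9.6.8. Only a direct link between each absent form and its reason is missing, and an analyst can supply that as one line.
- The Cycle 1 Day 4 form would cost an amendment. Its single weekly rating cannot separate monitored from pre-treatment days, and it may include inpatient time for subjects already admitted.

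**Conclusion.** No change to the plan is needed. With a 14- to 21-day interval, the past-week items at C2D1 cover 0 of 28 infusion days and 0 of 3 monitored days of cycle 1. This rests on the interval being kept. If C2D1 were held to the day 1 calendar after an interruption longer than 7 days, some infusion days could enter, up to all 7 recalled days at a 14-day interruption.

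The result is a valid single-arm description of status after one outpatient cycle in subjects who start cycle 2. It is not a measure of life on the pump or during home monitoring, and the study report should not present it as one. That is a matter of careful reporting: none of the suggested wording alters an estimate, an interval or a decision. How many subjects fall out before C2D1 cannot be judged from the documents, but the planned accountability and exposure summaries should show most of it.
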